---

## Study Summary

Title	Monitoring SARS-CoV-2 Vaccines and COVID-19 Related Outcomes in Individuals with Multiple Myeloma
Short Title	COVID19 Outcomes in Myeloma and the Impact of Vaccines (COSMIC)
Keywords	Myeloma, COVID-19, Vaccine, COSMIC
Sample Size	200 subjects
Study Population	Individuals with multiple myeloma will be enrolled in the United States
Duration	Duration of participation in the study will be approximately six months
Enrollment Period	Up to two years
Study Design	Multicenter
Primary Objective	Establish feasibility of clinical and patient-reported data collection related to SARS-CoV-2 vaccines, COVID-19 related outcomes, and overall health status in a decentralized, real-world evidence study for patients with multiple myeloma currently undergoing therapy.
Secondary Objective	Monitor incidence of COVID-19 infection requiring hospitalization and related outcomes in participants using electronic patient reported outcomes and participant-permissioned electronic health record data capture.
Inclusion and Exclusion Criteria	
Inclusion Criteria
 
 
• Diagnosis of multiple myeloma per the International Myeloma Working Group and currently receiving active treatment for any phase of the disease, including initial therapy, maintenance, or relapsed disease.
 
• Access to the internet
 
• An active patient portal (or willingness to activate)
 
• Willing to electronically sign the study-specific informed consent and authorization form
 
 
Exclusion Criteria
 
 
• Non-English speaking
 
• Lack of internet access
 
• Cognitive impairment precluding ability to provide informed consent
 

## 1 Introduction

### 1.1 Background and Study Rationale

The COVID-19 pandemic has had an outsized impact on individuals with underlying social and medical vulnerability, leading to increased rates of severe disease, hospitalization, and death in these groups. Participants with underlying immune compromise, such as those with multiple myeloma, represent one such group. The advent of vaccines against SARS-CoV-2 has significantly limited morbidity and mortality across all groups, but the effectiveness of vaccination in individuals who are less likely to mount sufficient antibody response is uncertain. For this reason, booster vaccines have been recommended for those with underlying immune compromise. However, several key gaps remain in our understanding of how to best protect these individuals.

There is a dearth of real-world evidence about the effectiveness of vaccination and boosters in patients who are immunocompromised, and very little information specifically about the recently approved mRNA boosters. Additionally, rates of vaccination and booster uptake in the United States remain low. A rapid, decentralized method of ascertaining information related to booster vaccine response and adverse events related to vaccines and COVID-19 infection is critical not only to answer questions about the booster vaccines, but to develop an infrastructure for answering similar questions about future vaccines or other diseases.

## 2 Study Objectives

- Establish feasibility of clinical and patient-reported data collection related to SARS-CoV-2 vaccines, COVID-19 related outcomes, and overall health status in a decentralized, real-world evidence study network for patients with multiple myeloma currently undergoing therapy.
- Monitor COVID-19 related outcomes in participants using electronic patient reported outcomes (PRO) and participant-permissioned EHR data capture.

### 2.1 Investigational Plan

The purpose of this project is to implement and establish the feasibility of a decentralized real-world evidence study network for patients with multiple myeloma and to monitor outcomes related to COVID-19 infection in this immunosuppressed population. Subjects with multiple myeloma will be invited to participate. The electronic portal will handle all consenting activities. Participants will be asked to complete specific study procedures electronically, including permission for EHR data transfer. Participants will be asked to complete electronic questionnaires periodically.

### 2.2 Study Endpoints

- **Primary endpoint:** Feasibility of obtaining baseline, 30-day, and 6-month clinical and PRO data capture from 200 consented patients.
- **Secondary endpoints:**
  - Percent of patients who enroll on the study platform who had previously received a SARS-CoV-2 booster.

- Percent of patients who enroll on the study platform who went on to receive a SARS-CoV-2 booster after enrollment.
- Percent of patients providing patient reported outcomes (PROs) at each timepoint.
- Among patients providing PROs, percentage for which PROs were viewed by site personnel.
- Percent of patients reporting COVID-19 infection confirmed by home-based or other testing.
- Patient-reported adverse outcomes related to confirmed COVID-19 infection (*as applicable*).
- Hospitalization or death related to COVID-19 as ascertained by full EHR data transmission provided by permission from the patient (*as applicable*).

### **3 Study Design**

#### **3.1 Study Population and Duration of Participation**

Up to 200 participants will be enrolled at up to 10 sites in the United States. Duration of participation in the study will be approximately six months.

#### **3.2 Inclusion Criteria**

1. Diagnosis of multiple myeloma per the International Myeloma Working Group and currently receiving active treatment for any phase of the disease, including initial therapy, maintenance, or relapsed disease.
2. Access to the internet.
3. An active patient portal (or willingness to activate).
4. Willing to electronically sign the study-specific consent and authorization form.

#### **3.3 Exclusion Criteria**

1. Non-English speaking.
2. Lack of internet access.
3. Cognitive impairment precluding ability to provide informed consent.

#### **3.4 Subject Recruitment**

Participants will be informed of the study by site physicians, other site personnel, or ASH Research Collaborative recruitment materials. The importance of SARS-CoV-2 booster vaccination in patients with multiple myeloma will be discussed/presented. Potential participants will be directed to the study application to learn more and provide consent if interested. Information about the study may be shared with participants by their care team in-person or virtually, through patient advocacy groups, or other IRB approved advertising mechanisms. Participants may also be contacted by IRB approved letter, social media, email, patient portal, textbacks, or phone call.

### **4 Study Procedures and Schedule of Events**

#### **4.1 Informed Consent**

Before initiating any study procedures, subjects will review an electronic version of the informed consent and authorization using the link and/or QR code provided. Upon reviewing the form, the subject

will provide his/her/their electronic signature. A signed copy of the consent will be available to the subject upon signing.

#### 4.2 Electronic Health Record Data Transmission

The following variables to be obtained from the electronic health record, include elements that fall under the categories below, as available through routine clinical practice or obtained as part of this study:

- Diagnoses and disease status
- Pathology
- Laboratory results
- Clinical features
- Co-morbid conditions
- Multiple myeloma related treatments

#### 4.3 Patient-Generated Health Data

Subjects will be asked to complete questions specific to their health as outlined below. All questions will be administered electronically through the study application. These measures will be obtained to establish health status and COVID-19 infection(s) acquired after study entry. These measures will be included at baseline and at specified timepoints, as outlined in the [Schedule of Activities](#).

The following patient-generated health data (PGHD) will be collected directly from the participating patient and are specified in [Appendix A](#):

- Study eligibility questions
- Contact information and socio-demographics
- Multiple myeloma diagnosis and disease status
- SARS-CoV-2 vaccination history
- Documented COVID-19 infections and treatments
- COVID-19 specific questions

Participants may request additional information about COVID-19 booster vaccinations. Sponsor will receive notification that a participant has requested additional information. Sponsor will also monitor participant requests.

#### 4.4 Patient Reported Outcomes

Subjects will be asked to complete standardized PROs specific to their quality of life as outlined below. All questions will be administered electronically through the study application. These measures will be obtained to establish feasibility of routine PRO capture. These measures will be included at baseline and at specified timepoints, as outlined in the [Schedule of Activities](#):

##### Quality of Life PROs

- European Organisation for Research and Treatment of Cancer (EORTC) QLQ-MY20
- European Organisation for Research and Treatment of Cancer (EORTC) QLQ-C30

Participants will be reminded electronically, if needed, to complete PROs and questionnaires at Day 0, Day 30, and Day 180 as scheduled. Reminders will be provided in advance of the window, and then weekly until completed.

Health care personnel at sites where participants receive care may be asked to review PROs as part of routine care. The number of unique health care personnel and the number of unique geographic sites from where the PRO portal is accessed will be recorded.

#### 4.5 Schedule of Activities

	Time 0 Screening, Consent, and Baseline	Time 1	Time 2
Activity	Day 0	Day 30 + 15 days	Day 180 + 30 days
Study ICAF	X		
EHR Data Transmitted	X	X	X
PGHD	X	X	X
PROs	X	X	X

### **Time 0 (Screening, Enrollment, and Baseline)**

The following procedures will be performed at the time of screening and enrollment and will be completed virtually:

- Study ICAF
- EHR data transmission
- PGHD
- PROs

### **Time 1**

Time 1 will occur 30 days (+ 15 days) following baseline and the following will be completed virtually:

- EHR data transmission
- PGHD
- PROs

### **Time 2**

Time 2 will occur 180 days (+ 30 days) following baseline and the following will be completed virtually:

- EHR data transmission
- PGHD
- PROs

## **4.6 Subject Withdrawal and Early Termination**

Subjects may withdraw from the study at any time without impact to their care. It will be documented whether or not each subject completes the study.

## **5 Statistical Considerations**

The accrual goal for this study is the enrollment of 200 participants, defined as eligible subjects who access the portal and consent to participate. The primary end point of this study is the proportion of consented participants who provide responses for the PRO instruments; we will separately track the proportion of consented participants who permission access to clinical data through the EHR. We will estimate the proportions and present them descriptively, with a point estimate and an exact binomial confidence interval at each of the PRO time points (Baseline, Day 30, and Day 180). We will also present descriptively the proportion of consented participants who permission EHR access.

We will also report descriptive statistics for each of the secondary objectives, including the proportion of participants who had received a SARS-CoV-2 booster prior to enrollment; the proportion who received a SARS-CoV-2 booster after enrollment; the incidence of patient-reported COVID-19 infection confirmed

by home-based or other testing (per patient report); and the incidence of patient-reported adverse outcomes related to confirmed COVID-19 infection, including long COVID.

Lastly, we will report descriptive statistics on the incidence of hospitalization (at the primary institution at which the patient received myeloma care) or death related to COVID-19 during the 6-month period of observation. We will report estimates for these metrics from two forms of ascertainment: patient-permissioned EHR data transmission and site-provided EHR data abstraction (received under the Data Hub's overarching umbrella protocol). We may perform exploratory analyses of clinical and laboratory correlates of severe adverse COVID-19 related outcomes, sample size permitting, based on site-provided EHR data abstraction (under the Data Hub's umbrella protocol).

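### Section 2.2 makes clinical and PRO capture the primary endpoint; Section 5 counts PRO response only, so the planned primary analysis answers only part of the primary objective

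*Combined protocol and SAP*

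**What the plan says.** Section 2.2 gives the primary endpoint as "Feasibility of obtaining baseline, 30-day, and 6-month clinical and PRO data capture from 200 consented patients". Among the secondary endpoints, the same section lists "Percent of patients providing patient reported outcomes (PROs) at each timepoint".

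Section 5 gives a different primary endpoint: "The primary end point of this study is the proportion of consented participants who provide responses for the PRO instruments". The sentence continues, "we will separately track the proportion of consented participants who permission access to clinical data through the EHR". Estimates are to be presented "with a point estimate and an exact binomial confidence interval at each of the PRO time points (Baseline, Day 30, and Day 180"). The section then adds, "We will also present descriptively the proportion of consented participants who permission EHR access". No confidence level, expected rate or feasibility threshold is stated.

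The first objective in Section 2 is wider than either endpoint: "Establish feasibility of clinical and patient-reported data collection related to SARS-CoV-2 vaccines, COVID-19 related outcomes, and overall health status".

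On the meaning of PRO, Section 4.4 says, "Subjects will be asked to complete standardized PROs specific to their quality of life as outlined below", and the list that follows holds only the EORTC QLQ-MY20 and QLQ-C30. Section 4.3 and Appendix A place vaccination history, COVID-19 infections and the COVID-19 questions under PGHD. The Schedule of Activities in Section 4.5 gives EHR data transmission, PGHD and PROs a row each, all three due at Day 0, Day 30 and Day 180.

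**The concern.** The two sections name different quantities as primary, and the quantity that Section 5 calls primary is secondary in Section 2.2. The Section 2.2 primary endpoint has no matching analysis. Because nothing says which section governs, the headline result could be chosen after the data are seen.

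What Section 5 counts also matters. On the protocol's own definitions it counts two quality-of-life questionnaires. Feasibility is the main purpose of the study (Section 2.1), and the objective names vaccine and COVID-19 data, yet the questionnaire that collects them has no planned capture rate. Without that rate, a reader also cannot judge how complete the patient-reported infection results are. For clinical data, permission to access a record is an earlier step than receiving data from it, and Section 4.5 schedules transmission at each of the three visits.

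**Working it through.** **Side by side.** For each data stream:

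| Stream | First objective (Section 2) | Primary endpoint, Section 2.2 | Scheduled at all three visits (Section 4.5) | Primary endpoint, Section 5 | Other capture measure in Section 5 |
|---|---|---|---|---|---|
| PROs (QLQ-C30, QLQ-MY20) | Yes, as patient-reported data on health status | Yes | Yes | Yes | None needed |
| Clinical (EHR) data | Yes | Yes | Yes | No | Proportion giving permission |
| PGHD (vaccine and COVID-19 questions) | Yes, as patient-reported vaccine and COVID-19 data | Not named | Yes | No | None |

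Section 5 reports some of the content of the third stream (infections per patient report, for example) but not how many participants supplied it.

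**Precision.** The plan has no figure to reproduce, since 200 participants is given without a derivation. Its exact binomial interval, taken at an assumed 95% level with n = 200, gives:

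- 160/200 = 80%: 73.8% to 85.3%, half-width about 5.8 points
- 140/200 = 70%: 63.1% to 76.3%, half-width about 6.6 points

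Precision is adequate. The difficulty is what is counted.

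**How far the PRO rate can lie from joint capture.** For k proportions, the share of participants with all k lies between max(0, sum of the proportions − (k − 1)) and the smallest of the proportions. Independence gives their product. All rates below are assumptions.

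1. One visit, PRO 80%, PGHD 80%, EHR 70%:
   - lower bound 0.80 + 0.80 + 0.70 − 2 = 0.30
   - upper bound min(0.80, 0.80, 0.70) = 0.70
   - independence 0.80 × 0.80 × 0.70 = 0.448
   - of 200 participants, 60 to 140 would have all three, while the Section 5 primary result would be 160/200
2. The same rates, with PRO and PGHD always returned together, so that only PRO and EHR can differ:
   - lower bound 0.80 + 0.70 − 1 = 0.50
   - upper bound 0.70
   - independence 0.80 × 0.70 = 0.56
3. PRO and EHR only, as in Section 2.2, at 80% each:
   - lower bound 0.80 + 0.80 − 1 = 0.60
   - upper bound 0.80
   - independence 0.80 × 0.80 = 0.64
4. PROs alone over the three visits, at 90%, 80% and 70%:
   - lower bound 0.90 + 0.80 + 0.70 − 2 = 0.40
   - upper bound 0.70
   - independence 0.90 × 0.80 × 0.70 = 0.504

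The PRO rate therefore does not determine the Section 2.2 quantity, and three per-visit PRO rates do not determine the share with complete follow-up.

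**The case against.** The best reply is that Section 5 does not ignore clinical data. It commits twice to reporting EHR permission, and its plural wording on estimating proportions may extend the exact intervals to that measure. It also uses EHR data, from patient permission and from site abstraction, for COVID-19 hospitalization and death. Separate components are a legitimate way to report feasibility, and they show which stream fails. The analysis is descriptive with no success rule, so no formal decision turns on the definition. All of this stands, and it rules out saying that clinical data are dropped. It leaves the conflict between the two definitions untouched, and permission is still not receipt.

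A second reply is that the objectives use PRO more loosely: the second objective in Section 2 says COVID-19 outcomes will be monitored through electronic PROs. That makes a broader reading possible. However, Sections 4.3 to 4.5 separate PROs from PGHD, and Section 5 refers to PRO instruments. The ambiguity is a further reason to settle the text.

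A third reply is that high PRO completion with poor PGHD completion is unlikely. Both are completed in the same application at the same visits, Section 4.4 applies reminders to PROs and questionnaires together, and Section 9.2 lists all three streams under each visit payment. This is persuasive. Capture is probably positively associated, so the lower bounds are extreme cases and joint capture is more likely near the upper end. Even so, the upper end in the first example is the assumed EHR rate of 70%, not the PRO rate of 80%.

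**Conclusion.** The primary endpoint is defined inconsistently between Sections 2.2 and 5. The Section 5 version, read with Sections 4.3 to 4.5, answers only part of the primary objective. Missing are a PGHD completion rate, EHR data received at each visit, and any joint measure. These conclusions rest on the text alone. The size of any gap does not: with assumed rates of 80%, 80% and 70%, joint capture is 30% to 70%, probably toward the top of that range, and the documents supply no rates to narrow it.

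Stronger readings are not supported:

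- A reader might infer that Section 5 omits vaccine and COVID-19 data named in the Section 2.2 primary endpoint. That endpoint does not name them; the primary objective does.
- A reader might infer that the primary analysis cannot answer the objective. PRO response at three visits together with EHR permission answers some of it.
- A reader might infer that an all-stream composite must be the sole primary endpoint. Neither section requires this, and co-reported proportions would also remove the conflict.

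**What to change.** Use one primary endpoint definition, worded identically in Sections 2.2 and 5. With all consented participants as the denominator:

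- at Day 0, Day 30 and Day 180, report the proportions with PROs completed, with PGHD completed and with EHR data received, each with an exact 95% confidence interval
- report the proportion with all three streams at each visit, and the proportion with all three at every visit
- keep EHR permission as a supporting measure
- list PRO-only completion once, not as both primary and secondary

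The cost is a change of wording and a few more descriptive proportions. All three streams are already scheduled at every visit, so no new data collection is needed. The drawback for the sponsor is that the joint figure cannot exceed the PRO-only figure and will probably be lower.

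### The primary endpoint spans baseline, 30 days and 6 months, but Section 5 estimates only three per-time-point PRO proportions, which repeat a secondary endpoint and leave the full-series share unestimated

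*Combined protocol and SAP*

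**What the plan says.** Section 2 gives the first objective as "Establish feasibility of clinical and patient-reported data collection related to SARS-CoV-2 vaccines, COVID-19 related outcomes, and overall health status". Section 2.2 turns this into one primary endpoint: "Feasibility of obtaining baseline, 30-day, and 6-month clinical and PRO data capture from 200 consented patients". Among the secondary endpoints, the same section lists "Percent of patients providing patient reported outcomes (PROs) at each timepoint".

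Section 5 restates the primary endpoint more narrowly: "The primary end point of this study is the proportion of consented participants who provide responses for the PRO instruments". Its estimate is descriptive, "with a point estimate and an exact binomial confidence interval at each of the PRO time points (Baseline, Day 30, and Day 180". Clinical data sit outside this proportion: "we will separately track the proportion of consented participants who permission access to clinical data through the EHR".

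On numbers, Section 5 says "The accrual goal for this study is the enrollment of 200 participants", and Section 3.1 treats 200 as a ceiling. No confidence level, expected response rate, precision target or feasibility threshold is given. Section 4.5 schedules both PROs and EHR transmission at all three times. Section 4.6 says that each subject's completion of the study will be documented, but it does not define completion as three-point capture, and no analysis uses it.

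**The concern.** Two things do not fit together.

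- **Overlap.** The only analysis that Section 5 gives for the primary PRO endpoint is the same set of percentages that Section 2.2 lists as secondary. As written, the primary endpoint adds nothing to that secondary one.
- **A missing quantity.** An endpoint that names three times in one phrase suggests interest in the series. Three separate proportions cannot recover it, because the people missing at Day 30 need not be those missing at Day 180.

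What is at stake is how informative the feasibility result is. The study is meant to show that a decentralized network can follow patients with myeloma for about six months. Followed exactly, the plan reports response at each time but not how many participants have a usable baseline, 30-day and 6-month record.

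**Working it through.** **Inputs.** n = 200 is the accrual goal in Section 5. It comes with no design inputs, so there is no sample-size calculation to reproduce. The 95% level is an assumption, because Section 5 does not state one. All response rates are assumptions; the main case is p0 = 95%, p30 = 80% and p180 = 70%, that is 190, 160 and 140 of 200.

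**Step 1: what the plan would report.** Exact (Clopper-Pearson) 95% intervals at n = 200:

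| Time | Responders | Estimate | Exact 95% CI |
|---|---|---|---|
| Baseline | 190 | 95% | 91.0–97.6% |
| Day 30 | 160 | 80% | 73.8–85.3% |
| Day 180 | 140 | 70% | 63.1–76.3% |

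**Step 2: what these figures imply for the full series.** For any three proportions, max(0, p0 + p30 + p180 − 2) ≤ p_all ≤ min(p0, p30, p180).

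- Lower bound: 0.95 + 0.80 + 0.70 − 2 = 0.45, or 90 of 200.
- Upper bound: min(0.95, 0.80, 0.70) = 0.70, or 140 of 200.
- Independent responses: 0.95 × 0.80 × 0.70 = 0.532, or about 106 of 200 (exact 95% CI for 106/200: 45.8–60.1%).
- Positive dependence (trivariate normal, common latent correlation 0.3, 0.5, 0.7, 0.9): 57.6%, 60.7%, 64.1%, 68.0%.
- Monotone dropout: 70%, equal to the Day 180 proportion.

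The monotone case can be checked by counting. Let 140 participants respond at all three times, 20 at baseline and Day 30 only, 30 at baseline only, and 10 never. The totals are 140 + 20 + 30 = 190, 140 + 20 = 160, and 140. The table in Step 1 is therefore the same whether 140 or about 106 participants have the full series.

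**Step 3: how far the low end can be believed.** The misses number 10 + 40 + 60 = 110. A share of 45% (200 − 110 = 90) requires that nobody misses more than one assessment. A single participant who withdraws before Day 30 and so misses both later assessments breaks that condition. The 45% is a bound, not a scenario; 53% to 70% is the more useful range.

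**Step 4: other assumed rates.**

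| Assumed rates | Bounds | Independent |
|---|---|---|
| 90/75/65% | 30–65% | 0.90 × 0.75 × 0.65 = 43.9% |
| 95/85/80% | 60–80% | 0.95 × 0.85 × 0.80 = 64.6% |

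**Step 5: precision of the added estimate.** With all 200 consented participants as denominator, the widest exact 95% interval is at 100/200: 42.9–57.1%, a half-width of about 7.1 points. At 140/200 it is 63.1–76.3%. If accrual stops short of 200, the intervals widen.

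**The case against.** The strongest reply is that Section 2.2 nowhere requires the three captures to come from the same participant. Its list of times can be read as the occasions on which capture is assessed, and Section 5 does exactly that. This stands, so the two sections are not proven to contradict each other. The reply leaves the overlap untouched, however: on that reading the primary PRO analysis and the listed secondary endpoint are the same thing.

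A second reply is that the full-series share may differ little from the Day 180 figure. If people who miss Day 30 mostly miss Day 180 as well, the gap is small (68% against 70% at latent correlation 0.9). That is fair, but the plan does not assume monotone dropout, and nothing in the schedule makes Day 180 depend on completing Day 30.

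A reader might also infer that feasibility could be claimed from whichever time point looks best. The documents do not support this. Section 5 commits to an estimate and interval at every time point, so a weak Day 180 result would be visible. There is no test or success threshold, so no error rate is inflated.

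**Conclusion.** The point holds as a gap in estimation and a primary/secondary overlap. Section 5 does not produce the share of consented participants with the full PRO series, and its primary PRO analysis coincides with a secondary endpoint. Under assumed rates of 95/80/70% and n = 200, the unreported share lies between about 53% (independent) and 70% (monotone dropout), with 45% a mathematical floor. These sizes rest wholly on the assumed rates and dependence; the documents supply neither.

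A reader might go further and say that Section 5 contradicts Section 2.2, or that a lower confidence limit should decide feasibility. The wording of Section 2.2 is too open for the first. The second has no footing, because the documents contain no threshold to compare a limit with. There is one further difference between the sections: Section 2.2 names clinical as well as PRO capture, while Section 5 keeps EHR permission apart and does not tie it to the three times. For a descriptive observational study this is an inexpensive improvement, not a flaw that undermines the study.

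**What to change.** In Section 5:

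1. Add, as the primary summary, the proportion of consented participants who provide the PRO instruments at all three times (Baseline, Day 30 and Day 180), with an exact binomial 95% confidence interval.
2. Keep the three per-time-point proportions as the secondary endpoint that Section 2.2 already lists.
3. Report the same all-three proportion for PRO plus EHR data, since the Section 2.2 endpoint covers both and Section 4.5 schedules EHR transmission at each time.

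The cost is a few sentences and two further proportions from data already scheduled for collection; no extra patients or visits are needed. The drawback is presentational: the all-three figure cannot exceed the lowest time-point proportion, and the PRO-plus-EHR figure cannot exceed the all-three PRO figure, so the headline will look less favourable.

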### 9.2 Subject Payments

Modest remuneration will be provided to participants in the study to help defray the cost of participation. The following represents the projected compensation scheme for each subject; however, payments may be made in installments that accommodate participant scheduling.

Subjects will receive up to a total of \$400 for completing all study visits:

- **Time 0:** \$200 upon completion of enrollment activities (study ICAF, EHR data transmitted, PGHD, and PROs)
- **Time 1:** \$100 (EHR data transmitted, PGHD, and PROs)
- **Time 2:** \$100 (EHR data transmitted, PGHD, and PROs)

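### Section 5 measures clinical data capture by EHR permission, so the clinical half of the Section 2.2 primary endpoint is never estimated at Day 0, Day 30 or Day 180

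*Combined protocol and SAP*

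**What the plan says.** The relevant statements in the combined protocol and SAP are these.

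- **Section 2.2 (Study Endpoints)** gives the primary endpoint as "Feasibility of obtaining baseline, 30-day, and 6-month clinical and PRO data capture from 200 consented patients". Clinical data and PROs stand side by side, at three timepoints.
- **Section 4.5 (Schedule of Activities)** has a row "EHR Data Transmitted", marked at Day 0, Day 30 (+15 days) and Day 180 (+30 days).
- **Section 9.2 (Subject Payments)** attaches the Time 1 and Time 2 payments to "EHR data transmitted, PGHD, and PROs". The Time 0 payment also lists transmission.
- **Section 5 (Statistical Considerations)** restates the endpoint: "The primary end point of this study is the proportion of consented participants who provide responses for the PRO instruments". On clinical data it continues: "we will separately track the proportion of consented participants who permission access to clinical data through the EHR". Proportions are to be given "with a point estimate and an exact binomial confidence interval at each of the PRO time points (Baseline, Day 30, and Day 180"). The EHR measure then has its own closing sentence: "We will also present descriptively the proportion of consented participants who permission EHR access".

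That closing sentence names neither a timepoint nor a criterion for receipt. Section 5 states no target rate, expected rate or success threshold for either proportion.

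**The concern.** Permission and capture are different events, and the protocol treats them so. Section 2.1 asks participants to permit transfer. Section 4.5 schedules transmission as a repeated activity, and Section 9.2 pays for it as a deliverable. Several things can intervene between the two. Section 3.2 accepts a patient who is merely willing to activate a portal, Section 4.6 allows withdrawal at any time, and Section 7.1 foresees revoked authorization.

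A feasibility study of a decentralized network should be able to show whether data keep arriving. If the plan is followed as written, the report will state how many people granted access and how many answered PROs. It will not state for how many participants clinical data came in at 30 days or 6 months. That is half of what Section 2.2 sets out to establish.

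There is also an effect on a secondary endpoint. Section 2.2 ascertains COVID-19 hospitalization or death through EHR transmission. Unless it is known whose records arrived through Day 180, a reader of that result cannot tell an absent event from an absent record.

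**Working it through.** **No plan figure to reproduce.** Section 5 gives 200 as an accrual goal ("The accrual goal for this study is the enrollment of 200 participants, defined as eligible subjects who access the portal and consent to participate"), with no power, precision or threshold calculation behind it. The check therefore compares the sections and then shows how large a gap could be under stated assumptions.

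**Step 1: endpoint against analysis.**

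| Component | Section 2.2 | Sections 4.5 and 9.2 | Section 5 |
|---|---|---|---|
| PRO data | three timepoints | scheduled and paid at three | proportion with exact interval at three |
| Clinical (EHR) data | three timepoints | transmission scheduled and paid at three | proportion granting access; receipt not analysed |

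**Step 2: how permission relates to receipt.** Let p be the share of consented participants who ever grant access, and t the share of those whose data arrive at a given timepoint.

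- Received = p × t
- Gap = p − p × t = p × (1 − t)

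Since t cannot exceed 1, p is an upper bound on receipt by this route. The two agree only when t = 1.

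**Step 3: illustration.** Inputs: n = 200 (Section 5), and exact Clopper-Pearson intervals, taken as two-sided 95% because Section 5 gives no level. Both p and t are assumptions; the documents supply neither.

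| Assumed p | Assumed t | Received | Exact 95% CI | Gap (points) |
|---|---|---|---|---|
| 0.85 | 1.00 | 170/200 = 85.0% | 79.3–89.6% | 0 |
| 0.85 | 0.90 | 153/200 = 76.5% | 70.0–82.2% | 8.5 |
| 0.85 | 0.70 | 119/200 = 59.5% | 52.3–66.4% | 25.5 |
| 0.90 | 1.00 | 180/200 = 90.0% | 85.0–93.8% | 0 |
| 0.90 | 0.95 | 171/200 = 85.5% | 79.8–90.1% | 4.5 |
| 0.90 | 0.90 | 162/200 = 81.0% | 74.9–86.2% | 9.0 |
| 0.90 | 0.60 | 108/200 = 54.0% | 46.8–61.1% | 36.0 |

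Over p from 0.70 to 0.95 and t from 0.60 to 1.00, the gap runs from 0 to 0.95 × 0.40 = 38 points.

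**Step 4: when the gap would matter.** At p = 0.85, receipt falls below the lower limit of the permission interval once non-delivery exceeds 1 − 0.793/0.85 = 6.7%. At p = 0.90, t = 0.95 gives a gap of 4.5 points, about the half-width of the permission interval (4.4 points). At p = 0.85 with 10% non-delivery, the intervals for permission and receipt still overlap (79.3–89.6% and 70.0–82.2%).

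**Step 5: all three timepoints.** With p = 0.90 and t = 0.90 at each visit, complete capture is 81.0% if the same people are missing every time. It is 0.90 × 0.90³ = 65.6% if losses are independent. Per-visit figures alone do not settle this, so the joint proportion needs its own line.

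**The case against.** The best defence is that Section 5 never calls permission capture. A proportion correctly labelled as permission overstates nothing; it leaves receipt unreported. The plan is also descriptive, with no test or decision tied to the EHR figure, and per-visit transmission could probably be tabulated from what is already scheduled and paid for. This limits the consequence but does not close the gap: in a descriptive study the estimate is the result, and the one Section 2.2 calls for is not specified.

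A second defence is that site-provided abstraction supplies clinical data anyway. Section 5 plans it for COVID-19 hospitalization and death and for exploratory analyses, under a separate umbrella protocol. It is not a feasibility measure, and it does not test the patient-permissioned route.

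A reader might infer four stronger points that the documents do not support:

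- **That permission is collected only once.** This is plausible but nowhere stated.
- **That clinical capture will be overstated.** The gap may be zero, and no rate is given from which to predict it.
- **That permission sets the denominator for EHR-based hospitalization.** Section 5 states no denominator for that endpoint, and it reports the endpoint from site abstraction as well.
- **That the EHR proportion definitely has no confidence interval.** The plural in Section 5's sentence on estimating proportions could cover both measures at each timepoint; the separate closing sentence suggests otherwise. The text is unclear. Even on the generous reading, the quantity estimated is permission.

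**Conclusion.** The point holds in this form: Section 2.2 puts clinical data capture at three timepoints into the primary endpoint, while Section 5 makes that endpoint PRO-only and measures clinical data by permission alone. Permission bounds receipt from above on the patient-permissioned route. It can therefore overstate capture, and it cannot show capture at Day 0, Day 30 or Day 180.

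The mismatch between the sections rests on the text and needs no assumption. The size of any gap rests wholly on assumed rates. With 85% permission and 10% to 30% non-delivery at Day 180, it would be 8.5 to 25.5 points; with full delivery it would be nil. The plan should be changed, but nothing here calls for a different accrual goal, since 200 rests on no calculation that this would alter.

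**What to change.** In Section 5:

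1. Keep the proportion granting EHR access, labelled as a first step.
2. Add the proportion of all consented participants with a patient-permissioned EHR transmission received in each scheduled window (Day 0; Day 30 +15 days; Day 180 +30 days), and the proportion with receipt in all three. Give each an exact binomial interval and state the confidence level.
3. Count a participant at a timepoint only if a new transmission arrived in that window. A rule satisfied by any record dated up to the timepoint would let a Day 0 transmission count at Day 180 and would hide a lost connection.
4. Define receipt on the data categories listed in Section 4.2. Encounter data are not among them, so requiring encounters would add a data element.
5. Report site-abstracted data separately.

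Reconcile Sections 2.2 and 5 on whether clinical data capture is part of the primary endpoint.

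**Cost.** Some wording, a check of each transmission against the definition, and a small extra tabulation, probably from records already needed for the Section 9.2 payments. The reported figure may be less favourable than permission alone.
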